## 7.2 GTB-3550 TriKE Dose Levels

### 7.2.1 Dose Finding Component (Phase I)

The 1st two patients will be assigned dose level 1. The study statistician (UMN biostatistician [name] or designee) will assign each new cohort of 2 patients to the most appropriate dose level based on updated toxicity probabilities. Both patients within a dose cohort must reach Day 28 (end of the DLT assessment period) prior to enrollment of a subsequent cohort. Enrollment continues until 30 evaluable patients are accrued.

Dose Level	GTB-3550 TriKE Dose daily continuous infusion (CI) dose ( $\mu$ g/kg/day)
1	5
2	10
3	25
4	50
5	100
6	150
7	200

**Dose Limiting Toxicity (DLT)** is defined as any of the following related treatment emergent toxicity with the exception of those that are clearly and incontrovertibly due to extraneous causes within 28 days (**as assessed on Day 29**) of the first dose of TriKE for the following criteria based on CTCAE v5:

- Any Grade 4 or 5 non-hematologic events
- Grade 3 non-hematologic adverse events lasting more than 72 hours, except the following:
  - Non-sustained (< 7 days) Grade 3 liver function tests (ALT/AST, alkaline phosphatase, total or direct bilirubin) abnormalities in the absence of clinical signs of hepatic dysfunction (lethargy, confusion, anorexia, pruritus or tremors).
  - Non-sustained Grade 3 QTc prolongation (< 72 hours) in the absence of cardiac arrhythmia
  - Grade 3 electrolyte disturbances that resolve, with or without intervention, to < Grade 2 levels within 72 hours
  - Grade 3 fatigue
  - Grade 3 anorexia
  - Grade 3 fever
  - Grade 3 infection
- Hematologic Toxicity - Given that AML and MDS inherently leads to low neutrophils and platelets, standard grading cannot be used as many of these patients technically meet criteria for "Grade 4" neutropenia or thrombocytopenia at baseline. Thus, the hematologic DLTs are listed below:
  - AML
    - Grade 4 neutrophil count (< 500/ $\mu$ L) lasting  $\geq$  29 days from start of cycle in absence of evidence of active leukemia
    - Grade 4 platelet count (< 25,000/ $\mu$ L) lasting  $\geq$  29 days from start of cycle in absence of evidence of active leukemia
- Any clinically significant bleeding that is not controllable with transfusion support
  - MDS/mast cell diseases:
    - Grade 4 neutrophil count (<500/ $\mu$ L) lasting  $\geq$  29 days from start of cycle in absence of evidence of active MDS/mast cell disease
    - Grade 4 platelet count (<25,000/ $\mu$ L) lasting  $\geq$  29 days from start of cycle in the absence of active MDS/Mast cell disease
    - Any clinically significant bleeding that is not controllable with transfusion support
    - Grade 4 anemia, unexplained by the underlying disease

- Grade 3 infusion related, treatment related reaction including cytokine release syndrome which does not resolve within 72 hours despite best medical management (refer to [Section 10](#) for modified CRS grading)
- Grade 3 or 4 Tumor Lysis Syndrome that does not resolve within 7 days with or without intervention
- Inability to complete at least one block of three 24 hour infusions due to any treatment emergent, treatment related toxicity.

**Maximum Tolerated Dose (MTD)** is defined as the dose level that most closely corresponds to the target DLT rate of 20%.

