**Dose Finding Phase I Component:**

Each patient receives GTB-3550 TriKE at the assigned CI dose for 3 sets (infusion block #1, #2, and #3) of 4 consecutive 24 hours infusions separated by a 72 hour rest.

Dose Level	GTB-3550 TriKE Dose daily continuous infusion (CI) dose ( $\mu\text{g/kg/day}$ )
1	5
2	10
3	25
4	50
5	100
6	150
7	200

The phase I component uses a continual reassessment method (CRM). Patients are enrolled in cohorts of 2 beginning at Dose Level 1. A minimum of 1 week must separate each patient. Both patients within each cohort must reach Day 28 (end of the DLT assessment period) prior to enrollment of a subsequent cohort. The study statistician assigns each new cohort of 2 patients to the most appropriate dose level based on updated toxicity probabilities. As enrollment proceeds, each cohort will be assigned to an increased, decreased or equivalent dose level based on prior data in the trial. Enrollment continues until the study sample reaches evaluable 30 patients. At that time the maximum tolerated dose (MTD) for the Phase II component will be identified.

**Dose Limiting Toxicity (DLT)** is defined as any related treatment emergent toxicity within 28 days (as assessed on Day 29) of the first dose of TriKE with the exception of those that are clearly and incontrovertibly due to extraneous causes for the following criteria based on CTCAE v5:

- Any Grade 4 or 5 non-hematologic events
- Grade 3 non-hematologic adverse events lasting more than 72 hours, except the following:
  - Non-sustained (< 7 days) Grade 3 liver function tests (ALT/AST, alkaline phosphatase, total or direct bilirubin) abnormalities in the absence of clinical signs of hepatic dysfunction (lethargy, confusion, anorexia, pruritus or tremors).
  - Non-sustained Grade 3 QTc prolongation (< 72 hours) in the absence of cardiac arrhythmia
  - Grade 3 electrolyte disturbances that resolve, with or without intervention, to < Grade 2 levels within 72 hours
  - Grade 3 fatigue
  - Grade 3 anorexia
  - Grade 3 fever
  - Grade 3 infection

- Hematologic Toxicity - Given that AML and MDS inherently leads to low neutrophils and platelets, standard grading cannot be used as many of these patients technically meet criteria for “grade 4” neutropenia or thrombocytopenia at baseline. Thus, the hematologic DLTs are listed below:
  - AML:
    - Grade 4 neutrophil count (<500/ $\mu$ L) lasting  $\geq$  29 days from start of cycle in absence of evidence of active leukemia

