## 8 Schedule of Patient Activities

Scheduled evaluations after screening may be performed  $\pm 1$  day from the targeted date through Day 29; unless otherwise noted. A disease reassessment will occur between Days 21 and 42. A  $\pm 7$  day window is permitted for the end of treatment (EOT) visit. If a patient discontinues treatment before receiving all 3 blocks, subsequent time points are adjusted to maintain timing (i.e. Day 22 is moved to 1 week after the start of the last block).

In addition, targeted days may be altered as clinically appropriate. Follow-up visits are per standard of care with disease status and survival status abstracted from the medical record.

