The prior mean for the probability of DLT for the six doses (i.e. the power model skeleton) are 3%, 5%, 7%, 10%, 14% and 20%, respectively. As the study progresses, updated probabilities of DLT are computed before each new cohort of patients is enrolled and both patients of each cohort have reached Day 28 (end of the DLT assessment period) prior to enrollment of a subsequent cohort. Each subsequent cohort will be assigned to the most appropriate dose based on these updated probabilities. Eventually the final dose (within our proposed sample of 30 patients) will be identified as the dose most closely associated with a DLT rate of 20%. To promote patient safety: 1) we will enroll cohorts of 2 patients starting at the 1st dose; and 2) dose levels will not be skipped when escalating.

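### The next dose may be assigned at Day 28, before the Day 29 DLT assessment and before the 29-day neutrophil and platelet DLTs can be met, so such a DLT can be missed

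*Combined protocol and SAP*

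**What the plan says.** **Gate and model update.** Section 7.2.1 states: "Both patients within a dose cohort must reach Day 28 (end of the DLT assessment period) prior to enrollment of a subsequent cohort". The synopsis, the study schema and Section 4 repeat this. Section 12.1 says that "updated probabilities of DLT are computed before each new cohort of patients is enrolled and both patients of each cohort have reached Day 28".

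**DLT window.** The schema counts toxicity "within 28 days (as assessed on Day 29) of the first dose of TriKE", and Section 7.2.1 agrees. Section 10.3 gives the 28-day window without naming the assessment day.

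**Neutrophil and platelet DLTs.** For AML, a Grade 4 count must persist for at least "29 days from start of cycle in absence of evidence of active leukemia". For MDS and mast cell disease the platelet criterion reads at least "29 days from start of cycle in the absence of active MDS/Mast cell disease", and the neutrophil criterion is equivalent. Sections 7.2.1 and 10.3 and the schema all carry these criteria.

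**Timing of the supporting data.** Section 8 says: "A disease reassessment will occur between Days 21 and 42". Scheduled visits may move by one day either way ("day from the targeted date through Day 29; unless otherwise noted"). The schema requires at least one week between patients.

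**What is not stated.** The CRM text in Section 12.1 gives no weighting for incomplete follow-up and no rule for a hematologic DLT still pending when the dose is assigned.

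**The concern.** The stated gate comes before the stated assessment. On Day 28 a count criterion of at least 29 days cannot yet be satisfied, so a patient on course for this DLT can enter the model as having none. Read literally, an event that needs at least 29 days also cannot fall inside a 28-day window, which leaves it unclear whether the criterion can ever be triggered.

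The error has one direction: a DLT is recorded as no DLT, and the next assignment is the same or higher, never lower. The MTD is the primary Phase I output. It comes from 30 patients in pairs and becomes the Phase II dose, so the data behind each assignment should be complete or explicitly handled as incomplete.

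**Working it through.** The plan states no figure to reproduce here. The check is a day count followed by an illustration with the plan's CRM.

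**1. Day count** (Day 1 = first dose = start of cycle)

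| Day | Full days elapsed | Days counted inclusively | At least 29 days? |
|---|---|---|---|
| 28 | 27 | 28 | No, on either count |
| 29 | 28 | 29 | Inclusive count only |
| 30 | 29 | 30 | Yes, on both |

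The one-day window lets the Day 29 visit fall on Day 28, 29 or 30, so even a completed visit need not satisfy the criterion.

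**2. Which patient is affected.** With at least 7 days between patients, the first is at Day 28 + 7 = 35 or later when the second reaches Day 28. The first patient's duration criterion is then assessable. The duration gap therefore concerns the second patient only, by 1 to 2 days.

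**3. Disease status.** The reassessment window holds 42 − 21 + 1 = 22 days. Of these, 42 − 28 = 14 fall after Day 28 and 42 − 35 = 7 after Day 35. Status may be known at the decision, or may be pending for either patient.

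**4. CRM illustration**

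Inputs from Section 12.1: DLT probability at level i = (skeleton value)^exp(α), α ~ N(0, variance 0.5), target 20%, no skipping on escalation, and skeleton 3, 5, 7, 10, 14 and 20%.

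Assumptions: 17% (the value given for 150 µg/kg/day) is inserted as the sixth of seven skeleton values; there are two patients at each level reached; there are no DLTs at lower levels. The plan does not say whether the plug-in estimate or the posterior mean is used, so both were run. Plug-in estimates are skeleton^exp(posterior mean of α).

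*Level 1, one DLT in two patients counted as none*
- 1/2: exponent 0.475. Level 1 = 0.03^0.475 = 18.9%; Level 2 = 0.05^0.475 = 24.1%. Nearest to 20% is Level 1.
- 0/2: exponent 1.143. Level 7 = 0.20^1.143 = 15.9%, the nearest to 20%. The no-skip rule caps the move at Level 2.

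*Level 4, two DLTs counted as one*
- 2/2: exponent 0.615. Level 3 = 0.07^0.615 = 19.5%. Next cohort: Level 3 (25 µg/kg/day).
- 1/2: exponent 0.838. Level 5 = 0.14^0.838 = 19.3%; Level 6 = 0.17^0.838 = 22.7%. Next cohort: Level 5 (100 µg/kg/day).

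The posterior mean gives the same assignments in both examples.

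*Where nothing changes.* At Levels 3 to 7, 1/2 counted as 0/2 leaves the next CRM level unchanged under both estimators. At Level 4, for instance, the plug-in estimate for Level 5 falls from 19.3% to 5.0%, but both results assign Level 5. At Level 2 the result depends on the estimator: the plug-in estimate gives Level 3 either way, while the posterior mean gives Level 2 for 1/2 and Level 3 for 0/2.

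**5. A second route.** Section 7.2.1 also replaces doubling with a 50% increase once a single patient meets any DLT criterion. In that section's own example, the step after 50 µg/kg/day becomes 75 rather than 100. Absent another trigger, an uncounted DLT could leave this rule unapplied even where the CRM level is the same.

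**The case against.** A reader might infer that these DLTs can never be counted and always bias escalation upward. The documents do not support that.

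- **Stagger.** The first patient in each cohort is at Day 35 or later, so the duration criterion is already assessable there.
- **Day 28 is a minimum.** A decision taken after the Day 29 assessment complies with the gate and can count the event on an inclusive day count. The Revision 8 entry in the revision history, cited only as evidence of intent, describes moving on to subsequent patients at 29 days. With expected accrual of 1 to 2 patients per month, many decisions may fall later anyway.
- **Disease status.** The AML text asks for absence of evidence of active leukemia, not proof, and reassessment can begin at Day 21. Day 42 is the worst case.
- **Later recovery.** Toxicity probabilities are recomputed before each new cohort, and nothing bars a late DLT from the next update. A simulation that permanently reclassifies a random DLT as none would measure the wrong thing: the gap is mainly a delay, and only for two count criteria. Bleeding, Grade 4 anemia and non-hematologic DLTs are not affected.

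All of this stands and limits the point. It does not remove it. The text permits assignment at Day 28, nothing obliges the statistician to wait, and no rule covers a pending event or a refit.

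**Conclusion.** The inconsistency holds and should be corrected. At the earliest permitted decision, the second patient of a cohort cannot have met the neutrophil or platelet DLT on any day count. Either patient may have disease status pending.

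The consequence is conditional. One uncounted DLT can move the next cohort up by one level (Level 1 to Level 2) or by two (Level 3 to Level 5), and in several configurations it changes no CRM level. These examples rest on the 17% skeleton value, two patients per level and no earlier DLTs. The documents give no frequency for Grade 4 cytopenia of this duration without active disease, and it may be rare. No whole-trial effect on the MTD is claimed.

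**What to change.** Reconcile four items in the synopsis, the schema and Sections 4, 7.2.1, 10.3 and 12.1: the Day 28 gate, the 28-day window, the Day 29 assessment and the criterion of at least 29 days.

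1. Let the cohort gate and the CRM update follow both patients' completed Day 29 DLT assessment.
2. State one day-count convention under which the hematologic criterion can be met at that assessment, and make the visit window consistent with it.
3. In Section 12.1, state how a hematologic DLT with pending disease status enters the update, and that the model is refitted if a DLT is adjudicated later.

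This is a change of wording. It costs about one day per cohort: 30 patients in pairs make 15 cohorts and 14 transitions, so about 14 days over Phase I. It could take longer only where a Grade 4 cytopenia persists with disease status unresolved.

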### **7.1 GTB-3550 TriKE Administration**

Patients receive a single course of GTB-3550 TriKE at their assigned dose as 3 weekly treatment blocks. Each block consists of four consecutive 24 hour

continuous infusions (over approximately 96 hours) of GTB-3550 TriKE followed by a 72 hour break after Block #1 and #2. All treatment is given as an inpatient.

The assigned dose will be calculated on a weight obtained within 5 days prior to or on day of the 1st dose. The dose is not be recalculated for subsequent treatment blocks.

The institutional Investigational Pharmacy will prepare each 24 hour bag for infusion per [Section 9.6](#) based on the patient's assigned GTB-3550 TriKE dose. Each assigned dose will be administered as a 100 mL infusion over 24 hours period at 4.17 mL/hour rate. Note: actual bag volume is 130 ml to allow for the product sample collection before and after infusion.

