### 7.3 Management of Selected GTB-3550 TriKE Toxicities

Throughout the study, the investigator may prescribe any concomitant medications or treatment deemed necessary to provide adequate supportive care. Supportive care may include antibiotics, anti-fungals, analgesics, transfusions, and G-CSF/cytokines.

Note: Any patient experiencing a DLT equivalent toxicity must discontinue treatment per [Section 7.5](#) and is not eligible for retreatment.

Please refer to [Section 9.7](#) for potential toxicities.

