## 7.5 Duration of Study Treatment

Patients will receive one treatment course consisting of three sets (blocks) of four consecutive 24 hour continuous infusions GTB-3550 TriKE unless:

- the patient experiences the equivalent of a dose limiting toxicity (see [Section 7.2.1](#) for definition),
- the patient is unable to start Block #2 or #3 within 1 week of the planned date,
- the patient refuses further treatment,
- **Disease based treatment decisions:** If after completing Block #1 and Block #2, the patient has clear evidence of disease progression they will be discontinued from study treatment and further treatment with study drug is to be discontinued.
- In the opinion of the treating investigator, continuing treatment is not in the best interest of the patient.

For patients discontinuing prior to completing 3 blocks, post-treatment activities at Day 22 and Day 29 are shifted earlier to maintain the timing (i.e. 1 and 2 weeks from the start of the final block).

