## 10.2 Event Documentation

Event monitoring and documentation begins with the 1st dose of TriKEs.

For the purposes of this study, selected expected adverse events will be assessed using the Targeted Toxicity Worksheet ([Appendix VI](#)) and any unexpected events will be collected at the following time points in relation to the GTB-3550 TriKE infusions through Day 29:

- Prior to the infusion start of each 24 hour infusion (i.e. Day 1, 2, 3, 4, and Day 8, 9, 10, 11, and Day 15, 16, 17, 18)
- At the end of the final infusion of each block (i.e. Day 5, Day 12, Day 19)
- Day 22
- Day 29

At each time point, the worst grade of the targeted toxicity since the last assessment or the previous 24 hours (whichever is shorter) will be recorded in addition to any unexpected toxicities felt at least possibly related the study treatment.

If a patient discontinues study therapy early or otherwise does not receive treatment as planned, the targeted toxicity assessment time points may be adjusted or eliminated; however, patients must be assessed for a minimum of 28 days from the 1st dose of study drug.

If a patient is not abiding by the standard of care study calendar ([Section 8.1](#)), collection of the corresponding targeted events (and research related samples) also may be altered or discontinued on an individual patient basis, as appropriate.

Monitoring for adverse events will end after the last targeted assessment; however, the investigator is obligated, upon knowledge of, to report any event meeting the criteria in [Section 10.5](#).

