### **10.3 Dose Limiting Toxicity Documentation and Reporting (Phase I Dose Finding)**

The following events count toward dose limiting toxicity (DLT) during the Phase I dose finding component and must be reported the UMN Multisite Program Manager per [Section 10.6](#).

Note: DLT events are only reported for patients enrolled in the Phase I portion of the trial; however, any patient experiencing a DLT is not eligible to continue treatment per [Section 7.5](#).

A DLT is defined as a related treatment emergent toxicity that occurs within 28 days after the 1st TriKE dose with the exception of those that are clearly and incontrovertibly due to extraneous causes:

- Any Grade 4 or 5 non-hematologic events
- Grade 3 non-hematologic adverse events lasting more than 72 hours, **except** the following:
  - Non-sustained (< 7 days) Grade 3 liver function tests (ALT/AST, alkaline phosphatase, total or direct bilirubin) abnormalities in the absence of clinical signs of hepatic dysfunction (lethargy, confusion, anorexia, pruritus or tremors).
  - Non-sustained Grade 3 QTc prolongation (< 72 hours) in the absence of cardiac arrhythmia
  - Grade 3 electrolyte disturbances that resolve, with or without intervention, to < Grade 2 levels within 72 hours
  - Grade 3 fatigue
  - Grade 3 anorexia
  - Grade 3 fever
  - Grade 3 infection
- Hematologic Toxicity - Given that AML and MDS inherently leads to low neutrophils and platelets, standard grading cannot be used as many of these patients technically meet criteria for “grade 4” neutropenia or thrombocytopenia at baseline. Thus, the hematologic DLTs are listed below:
  - AML
    - Grade 4 neutrophil count (< 500/ $\mu$ L) lasting  $\geq$  29 days from start of cycle in absence of evidence of active leukemia

- Grade 4 platelet count (< 25,000/ $\mu$ L) lasting  $\geq$  29 days from start of cycle in absence of evidence of active leukemia
- Any clinically significant bleeding that is not controllable with transfusion support
- MDS/mast cell diseases:
  - Grade 4 neutrophil count (<500/ $\mu$ L) lasting  $\geq$  29 days from start of cycle in absence of evidence of active MDS/mast cell disease
  - Grade 4 platelet count (<25,000/ $\mu$ L) lasting  $\geq$  29 days from start of cycle in the absence of active MDS/Mast cell disease
  - Any clinically significant bleeding that is not controllable with transfusion support
  - Grade 4 anemia, unexplained by the underlying disease

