## 12 Statistical Considerations

### 12.1 Study Design and Endpoints

This is a multisite Phase I/II study of GTB-3550 trispecific killer cell engager (TriKE) for the treatment of high risk MDS and relapsed AML. Once the MTD is identified, the objective will be to confirm safety and obtain preliminary estimates of efficacy as measured by the objective response, the **primary trial endpoint** as assessed between Day 21 and Day 42. For AML clinical response includes complete remission with or without hematologic or platelet recovery (CR, CRi or CRp) or partial response. For MDS clinical response includes complete remission, marrow CR (with incomplete peripheral blood count normalization), partial response or hematologic improvement (HI). For advanced systemic mastocytosis response is considered a decrease in mast cell burden in bone marrow or serum tryptase level by at least 30%.

All patients completing Block #1 will be evaluable for DLTs and toxicities. Patients who discontinue therapy prior to completion of both Block #1 and Block #2 will be replaced. Patients completing Block #1 and Block #2, but come off treatment for disease progression, will still be evaluable for efficacy and will not be replaced. If needed a subgroup of patients receiving all 3 blocks will also be evaluated for response as a secondary population. We expect that the number of patients coming off therapy after only completing block #1 will be minimal.

**Secondary trial endpoints** will include toxicity through Day 29 and overall survival (OS) at 6 months from 1st dose of study drug.

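### The exposure DLT refers to three infusions although every block has four, and Section 12.1 does not say that patients stopped in Block #1 by toxicity enter the CRM

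*Combined protocol and SAP*

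**What the plan says.** On the length of a block, Section 7.1 of the protocol states: "Each block consists of four consecutive 24 hour" infusions, over about 96 hours, with a 72-hour break after Blocks #1 and #2. The last item of each DLT list (Study Schema, 7.2.1, 10.3) instead reads: "Inability to complete at least one block of three 24 hour infusions due to any treatment emergent, treatment related toxicity".

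On who counts, Section 12.1 says: "All patients completing Block #1 will be evaluable for DLTs and toxicities". It then says: "Patients who discontinue therapy prior to completion of both Block #1 and Block #2 will be replaced". The only case it exempts from replacement is progression after both blocks. The revision history (revision 9) records that the definition of evaluable and the replacement rule were placed in this section. Section 7.2.1 runs dose finding to 30 evaluable patients.

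On stopping, Section 7.3 says: "Any patient experiencing a DLT equivalent toxicity must discontinue treatment per" Section 7.5, and 7.5 ends the course when "the patient experiences the equivalent of a dose limiting toxicity".

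On counting, Section 10.3 says: "A DLT is defined as a related treatment emergent toxicity that occurs within 28 days after the" first TriKE dose, and states that the listed events count in Phase I. Section 10.2 adds that after early discontinuation "patients must be assessed for a minimum of 28 days" from the first dose. Neither section makes completion of a block a condition.

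**The concern.** There are two separate defects.

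The first is the number of infusions. Section 7.1 permanently stops drug for a second Grade 2 infusion reaction after restarting, or for any Grade 3 reaction. Section 7.2.1 makes a Grade 3 reaction a DLT only if it has not resolved within 72 hours. Suppose such a stop falls in the fourth infusion of Block #1 and meets no other DLT item. If three is a slip for four, the patient never completed a block and has a DLT. If three is a minimum exposure, the patient does not.

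The second matters more and does not depend on the first. A DLT forces the patient off treatment. If this happens in Block #1, the patient is outside the only group that 12.1 names as DLT-evaluable, and 12.1 calls for a replacement. Taken literally, 12.1 sets aside the very patients whom the exposure DLT is meant to capture. A statistician following 12.1 alone and one following 10.3 could feed the CRM different data from the same patients. Under the first approach the DLT rate is understated and dose assignment and the MTD drift upward. That dose is then carried into Phase II.

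**Working it through.** **Block length.** 4 × 24 h = 96 h, which reproduces the figure in 7.1; 96 + 72 = 168 h = 7 days, which matches weekly blocks. Three infusions would give 72 + 72 = 144 h = 6 days, which does not match. Four is the block length.

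**Size of the bias if Block #1 DLTs are left out.** Let p be the true DLT rate and f the share of DLTs that stop Block #1 and are omitted. The documents give no value for f, so a range is assumed.

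- Rate the CRM sees: p(1 − f)/(1 − pf). At p = 0.20: f = 10% gives 0.18/0.98 = 18.4%; f = 25% gives 0.15/0.95 = 15.8%; f = 50% gives 0.10/0.90 = 11.1%.
- True rate at a dose that appears to have 20%: 0.20/(1 − 0.8f) = 0.20/0.92 = 21.7%, 0.20/0.80 = 25.0%, 0.20/0.60 = 33.3%.

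**Simulated CRM.** Inputs from 12.1, 12.3 and 12.4: one-parameter power model; skeleton 3, 5, 7, 10, 14, 17, 20% (17% being the value given for 150 µg/kg); normal prior with mean 0 and variance 0.5; target 20%; cohorts of 2; no skipping; stop if the probability that Level 1 exceeds 20% is above 90%; 30 evaluable patients.

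Assumptions: true rate 20% at the MTD, with odds changing by 1.7 per level (the 12.3 odds ratio applied per step). This gives 4.8/8.0/12.8/20.0/29.8/41.9/55.1% for an MTD at Level 4 and 2.9/4.8/8.0/12.8/20.0/29.8/41.9% for Level 5. Replacement is at the same dose. The slower escalation after immune activation is not modelled. There were 12,000 trials per setting (Monte Carlo SE at most 0.5 points).

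Chance of selecting a dose above the true MTD, plug-in / posterior-mean estimate:

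| Handling of Block #1 DLTs | MTD Level 4 | MTD Level 5 |
|---|---|---|
| All counted | 28.4 / 27.9% | 29.6 / 26.7% |
| 10% of DLTs left out | 36.9 / 34.8% | 36.8 / 34.0% |
| 25% left out | 50.4 / 48.2% | 50.8 / 47.9% |
| 50% left out | 78.1 / 76.5% | 78.6 / 74.7% |
| 25% counted and replaced | 27.9 / 26.2% | 28.9 / 27.1% |
| 50% counted and replaced | 25.2 / 25.8% | 26.9 / 26.1% |

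The mean true DLT rate at the selected dose is 20.8-21.6% with all counted, and 22.6-23.3%, 25.8-26.7% and 33.1-34.8% with 10%, 25% and 50% left out. A smaller run (400 trials) with different assumed rates (3, 6, 12, 20, 32, 40, 48%) gave about 28%, 53% and 78% above the MTD for 0, 25% and 50% left out.

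**Other positions of the MTD.** If the skeleton itself is the truth, the MTD is Level 7 and no dose lies above it. In a run of 2,500 trials (plug-in) the mean true rate at the selected dose was 17.6% with all counted and 19.7% with 50% left out. With the MTD at Level 6 the chance of selecting above it went from 43% to 86%.

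**One omitted DLT, next dose only.** With 0/2 at all lower levels, compare 1/2 (counted) with 0/2 (left out).

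- Level 1: at 1/2 the estimated rate is 18.9% (posterior mean 21.0%) and the next cohort stays at Level 1; at 0/2 it is 1.8% (5.7%) and the cohort escalates to Level 2. If the patient is counted and a replacement without DLT is added (1/3), the posterior-mean rule stays at Level 1 but the plug-in rule also moves to Level 2.
- Level 2: the assignment differs only under the posterior mean (Level 2 against Level 3).
- Levels 3 to 7: no difference.

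**The case against.** The strongest reply is that the protocol, read as a whole, already counts these patients. Section 10.3 says the listed events count toward DLT, and one of them is failure to complete a block; that item would do nothing if non-completers were not evaluable. Section 10.2 requires 28 days of assessment after an early stop, and cohort opening depends on Day 28 rather than on finishing a block. Section 12.1 does not say that only completers are evaluable, nor that a replaced patient's data are removed, and the sentence after the replacement rule concerns efficacy. A patient who completes Block #1 and has a DLT in Block #2 is expressly DLT-evaluable. All of this stands. A reader might infer that the plan excludes Block #1 DLTs from the CRM; the documents do not support that.

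Three further inferences also fail:

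- That replacement by itself biases the MTD. It does not: counted and replaced gives 25-29%, against 27-30% with all counted.
- That the word three by itself introduces bias. If a minimum exposure was intended, the fourth-infusion stop is deliberately not a DLT.
- That the trial has already been affected. Nothing in the documents shows such a patient, and one omitted case usually leaves the next dose unchanged.

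The simulated effect also depends on an assumed f and on where the true MTD lies. Section 7.2.1 slows later dose increases after any DLT, a partial protection that the simulation leaves out.

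What remains is that the section defining evaluability lacks the clause the other sections imply, and that the DLT definition contains a number at odds with the treatment schedule.

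**Conclusion.** The point holds as an internal inconsistency in the definition and handling of the Phase I primary endpoint. It is not a demonstrated exclusion of patients. The three-versus-four wording affects only stops in the fourth infusion that meet no other DLT item. The evaluability wording is the more consequential part: the other sections favour counting Block #1 DLTs, but 12.1 taken literally leaves them outside its DLT-evaluable group.

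If they were left out, and the true MTD were Level 4 or 5, the chance of selecting too high a dose would rise from about 27-30% to 34-37%, 48-51% or 75-79% for omitted shares of 10%, 25% or 50%. These shares are assumptions, and the documents give no basis for choosing among them. With the MTD at the top level there is no higher dose to select. If the patients are counted, whether or not they are replaced, this bias does not arise. The plan should be clarified because the possible error runs toward higher doses and the remedy is small.

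**What to change.** 1. In the Study Schema, 7.2.1 and 10.3, change three to four in the exposure item. If a minimum exposure is intended, say instead that the patient must complete at least three of a block's four infusions. Keep the existing condition of at least one block. Do not add an exemption for liver-test holds under 7.3.3; that would be a new change to the DLT definition and needs its own decision.

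2. Add one sentence to 12.1: any patient who received GTB-3550 and had a DLT, or who stopped Block #1 for treatment-related toxicity, is DLT-evaluable and enters the CRM as DLT or non-DLT under 7.2.1, whether or not that patient is replaced for the efficacy analysis.

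The cost is a few words in three places and one sentence, submitted as an amendment. No design parameter changes. If counting these patients is already the practice, the edit only records it.
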